### Study Design

We will use mixed methods to evaluate implementation. To assess our primary implementation outcomes, we will conduct pre-implementation, mid-implementation and post-implementation key stakeholder interviews (Component A) with providers and staff. For patients, we will conduct baseline and follow-up surveys as well as interviews with a subsample of those patients who completed surveys (interview approximately every 3rd consented patient with completed survey). We will use administrative data from the medical record (CPRS and CDW) to capture use of the CV toolkit (CPRS template) and referrals to preventive services. We will use a non-randomized stepped wedge design to evaluate the roll out of the intervention and the change in referrals over time across the sites.

#### Nonrandomized Stepped Wedge Study Design for Implementation Trials.

The CV Toolkit project will use a nonrandomized stepped wedge design, which rely on sequential roll-out to participating sites over time, while using other sites as controls until they begin implementation. Consistent with our substantial prior experience using these designs in VHA and armed with complexity theory's recognition of nonlinearity of implementation, we will use *nonrandomized* stepped wedges (rather than randomized) given their suitability for studying implementation. This design acknowledges that sites are heterogeneous, face multiple constraints, and, as a result, are ready to adopt interventions at different rates. The modified design explicitly considers the timing of implementation spread and addresses the statistical issues introduced by lack of randomization in implementation starts and processes. We will analytically compensate for the design by collecting patient-, provider-, and site-level data that may be associated with timing of the adoption of each intervention. We will include three levels in our hierarchical nonrandomized stepped wedge models: (1) patient, (2) time of intervention (i.e., when a provider starts using the intervention), and (3) site. Outcomes of interest (e.g. referrals to Gateway, other health promotion program and/or specialist) are measured for all patients at each site within the given intervention time period.

Nonrandomized stepped wedge designs make efficient use of all data available for within-site and between-site comparisons. For the within-site comparison, sites act as their own controls in an evaluation that compares sites pre- versus post-implementation. The comparison examines sites as they cross-over from control to intervention states. The between-site comparison evaluates the intervention period for a site vs. all other intervention and control periods for all sites. By having these two types of comparison, the design improves on the validity of the

evaluation of the intervention, by accounting for historical time trends that may occur outside of the intervention and for site contextual characteristics that may affect site performance.

## **Risk to Subjects**

This study involves both Veteran (260 total across four sites) and VA Staff participants (60 total across four sites).

### ***Veteran involvement and Characteristics***

This 4-site research project aims to implement and evaluate the CV toolkit designed to increase identification of CV risk among women Veterans, enhance patient/provider communication about CV risk, and increase women Veterans engagement and retention in relevant health services including referrals to key health programs. We will recruit adult women Veterans who visit their women's health provider at one of the four study sites if a CPRS CV risk template was activated from their primary care visit or they attended the Gateway to Healthy Living program. As long as the woman Veteran patient is also able to give informed consent to complete our protocol, she is eligible to participate. We expect to approach up to 200 women Veterans per site over the study period in order to achieve a minimum of 65 women participants in the survey/interviews for CV toolkit at each site. Our goal is to have 260 women total (minimum 65 per site across 4 sites) engaged in the project over the course of the study. Participation includes a brief survey at baseline and six-month post-baseline, and for a subset of women, a brief qualitative interview (approximately every third consented woman with a completed survey will be approached for an interview for a minimum of 20 patient interviews at a site). Women will be consented at the time of the survey and interviews. The women will also be consented to link their responses to their medical records at the time of the survey.

We will also use medical record data (CPRS template data and CDW data) to evaluate the roll-out of the intervention and the referral rates at all sites. This data will be evaluated for all women patients seen by the providers in the study over the study period. The data will only be evaluated in the aggregate and will not be linked to the patient survey or interview data (unless medical record access consent is received at the time of the survey).

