The CV toolkit is an innovative care model that is proactive, patient-centered and personalized to each woman that comes to an appointment. A patient begins using the CV toolkit at check-in for her appointment when she is given the CV worksheet to fill out while waiting to see her provider. Patient education materials specifically on women and CV risk will be in the waiting room and exam rooms. The CV worksheet will be used to initiate the provider-patient discussion of CV risk, and her provider or another staff member will use the information to fill out the CV template in CPRS during or after the appointment. Depending on the site needs and preferences, a research assistant and/or the *Gateway* facilitator may help populate the CV template with the screener information. The patient and provider will collaboratively determine the next steps (i.e. *Gateway to Healthy Living*, other referral, or waiting) and the provider will document the action plan in the template. All participants will be offered the *Gateway to Healthy Living* program by providers or other staff member as engagement and support for the patient action plan.

After the appointment, each woman will be asked if she is willing to participate in the project for monitoring CV risks and choices and if she consents, she will complete a patient survey and a possible interview with the RA (every 3rd consented patient will be asked to participate in both a survey and interview). At the sites where it is not feasible to consent a woman immediately after her appointment, the research staff will generate a patient list of all women seen in the clinic who had a CPRS template activated during her visit. Based on that list, a sample of the women will be mailed a consent and survey (and every 3rd consented patient will be asked to participate in the interview). Follow-up surveys and interviews will be administered to all women who completed the baseline survey six months after the baseline survey.

Those women who are referred to the *Gateway to Healthy Living* program will be contacted by the program facilitator immediately to arrange the group meeting. The women will be considered engaged in the *Gateway to Healthy Living* program when she attends the first group meeting. Information on goal setting, behavior change intentions and participation in other services will be collected by the facilitator at the group meeting and at the follow-up phone calls.

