#### **Information from and about Veterans:**

Sources of patient data for this project includes (1) Utilization data on CV services used six months prior to the start of the intervention and over the course of the study program obtained from enrollees' medical records, (2) information provided by patient participants via surveys and interviews, and (3) The implementation facilitator will track participant utilization of the program. Information on goal setting, behavior change intentions and participation in other services will be collected by the facilitator at the group meeting and during follow-up phone calls and entered on a coded tracking sheet. Follow-up surveys will be administered to all women who completed the baseline survey six months after the baseline survey.

After consent, all enrolled participants in each project will complete a 30-minute survey, delivered in-person by a research assistant (RA) at baseline and six-months post-baseline. For sites where it is not feasible to reach all the eligible women in person, the surveys and information sheets will be mailed to the patients address listed in VISTA/CPRS. Patients who do not return surveys within a 2- week window will be sent a reminder post card and then mailed a second informed consent and survey packet by 4 weeks if no survey is received. The surveys focus on patient activation, health-related quality of life, satisfaction with treatment, and project specific measures. In addition, a subset of approximately 45 women Veterans in each study (every third consenting patient) will also be asked to complete an additional 20-minute

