In the pre-conditions transcripts, we will identify commonly shared knowledge, attitudes, and beliefs related to care model structures, processes, and effectiveness and the potential for effectiveness. In mid-implementation interview data, we will identify factors facilitating and impeding implementation of the care model, and strengths and weaknesses of the model as implemented. We will assess the extent to which components of the model are being implemented, and which components are efficient and easy to incorporate into routine care. We will explore whether particular components appear to be of limited value in improving care and examine clinic and provider characteristics associated with varying levels of care model implementation and effectiveness. In post-implementation interview data, we will take a summative approach to characterizing overall experiences of and perspectives on implementation, with a particular focus on recommendations for scale up and spread.

For providers, we will compare and contrast data from frequent users of the template with infrequent users, and track changes in perceptions about the utility and impact of the toolkit on clinical practice from pre-conditions to maintenance. We will also assess provider attitudes toward ease of referral to the *Gateway to Healthy Living* program, and provider perceptions of changes in patient awareness and activation. For patients, we will compare and contrast data from those who used *Gateway to Healthy Living* with those who did not, and those who used other services. In order to evaluate the patient impact of *Gateway to Healthy Living*, we will assess changes in patient perceptions of CV risk, self-efficacy, and activation.

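### Women recruited because they already attended Gateway can have a baseline taken after exposure in the assessment of Gateway's patient impact

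*Combined protocol and SAP*

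**What the plan says.** **Who is recruited.** Section 5.1, Veteran involvement and Characteristics, takes women who visit their women's health provider "if a CPRS CV risk template was activated from their primary care visit or they attended the Gateway to Healthy Living program". The implementation text in 5.1 (Site Selection, CV Toolkit, and REP Implementation Phases) describes a different order: "After the appointment, each woman will be asked if she is willing to participate in the project", or, where that is not feasible, a mailing to women on a list of template activations. Section 5.2 follows the same two paths and makes patients eligible at their first provider visit in the 15-month implementation period. It mentions women referred to Gateway, but not women who have attended it.

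**When Gateway exposure starts.** The implementation text counts a woman as engaged in Gateway "when she attends the first group meeting". A referred woman "will be contacted by the program facilitator immediately to arrange the group meeting".

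**When measurements are taken.** Follow-up is timed six months from the baseline survey, not from Gateway. Interviews come after the survey: "approximately every third consented woman with a completed survey will be approached for an interview". Under 5.2 a packet handed out in clinic may be returned by mail. Under 5.5 a woman who has not returned a mailed survey gets a reminder, then a second packet by 4 weeks.

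**What is assessed.** In 5.6, under Qualitative Analysis, Gateway users are compared with non-users and with users of other services. For Gateway's effect on patients, "we will assess changes in patient perceptions of CV risk, self-efficacy, and activation".

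**The concern.** A change attributed to Gateway needs a starting point before Gateway. The plan defines when exposure begins but never ties the first survey or interview to that moment, and one recruitment route selects on exposure having already happened. For a woman who enters that way, the first measurement already contains whatever the meeting did to her perceived risk, self-efficacy or activation, so her later change understates the effect.

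The comparison group does not remove this. A non-user has no Gateway meeting, so her baseline cannot follow one. The distortion therefore falls on one side of the comparison. As the plan stands, a reader of the results could not tell how many women it applied to.

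**Working it through.** The plan states no figure for this assessment, so there is none to reproduce. The check sets the texts side by side.

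1. **Template route, in person.** Visit, template, referral if any, then approach after the appointment. The first survey would usually precede the first Gateway meeting. This describes the usual flow; it is not a rule.

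2. **Gateway route.** Read literally, a woman who qualifies only by attendance is not eligible until she has attended. Her first survey therefore follows her first meeting, and so does her first interview, because interviews are drawn from women with a completed survey. The implementation text and 5.2 contain no matching route. Section 5.4, as available, lists criteria for staff only and does not settle the matter.

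3. **Mail returns.** The facilitator makes contact at once, while a mailed baseline can still be outstanding when the second packet goes out by 4 weeks, and an in-clinic packet has no return deadline tied to Gateway. The interval from contact to first meeting is not given. Overlap is possible but not shown.

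4. **Does the follow-up timing correct it?** No. Follow-up falls six months after the baseline survey, so a late baseline moves the follow-up later and leaves the starting point after exposure.

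5. **What a late baseline does to an average change.** This step applies only if a survey score is used. Let E be the Gateway effect at follow-up, f the share of Gateway users whose first measurement follows the first meeting, and c the share of E already present at that measurement (0 to 1). Assume the same E in both groups of users. Then

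   average effect seen among users = (1 − f) × E + f × (1 − c) × E = (1 − f × c) × E.

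   The documents give neither f nor c. With assumed values:
   - f = 0: 1.00 of E
   - f = 0.10, c = 0.5: 1 − 0.05 = 0.95 of E
   - f = 0.25, c = 0.5: 1 − 0.125 = 0.875 of E
   - f = 0.50, c = 0.5: 1 − 0.25 = 0.75 of E
   - f = 0.50, c = 1: 1 − 0.50 = 0.50 of E

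   These values show the direction and form of the loss. They do not estimate its size here.

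6. **What else uses this baseline?** The primary implementation outcomes come from staff interviews (5.1, Study Design). The stepped-wedge referral analysis uses record data on all women seen. Part (b) of the impact-focused evaluation in 5.6 is defined as change from enrollment and does not claim to be change from before Gateway. None of these depends on the order of baseline and Gateway.

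**The case against.** The Gateway clause is still governed by a visit to the women's health provider, and the described sequence runs from worksheet to visit, template and referral. On that sequence most baselines come before Gateway. This stands, and it limits the point to an exception. But the clause offers attendance as an alternative to template activation, so the exception is written into recruitment.

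A reader might infer that the mail route makes late baselines common. The documents do not support that. Being contacted to arrange a meeting is not attending one, and no meeting date is given. One passage (5.1, Adequacy of Protection from Risk) explains mailing by some women not attending the group promptly or at all, which suggests that mailed packets reach women with late or no exposure.

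A reader might also infer that the assessment lacks a defined measure. That goes too far. The sentence sits under Qualitative Analysis, where interview data are the natural source. Activation is in any case a survey domain, and the other two constructs may fall under the last item listed: "The surveys focus on patient activation, health-related quality of life, satisfaction with treatment, and project specific measures". At most, detail is missing there.

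It is fair to say that a qualitative comparison has no single estimate to re-run, so a with-and-without analysis suits only a survey score. It is also fair that facilitator tracking and consented record linkage might allow the order to be recovered. The documents do not say, however, that the date of the first meeting is captured.

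**Conclusion.** The point holds and is minor. Followed as written, the plan lets a measurement taken after exposure serve as the starting point for Gateway's patient impact, and only among Gateway users. This rests on reading the attendance clause as a recruitment route in its own right and on the absence of any rule about order in the recruitment, evaluation and analysis sections.

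The share of women affected cannot be derived and may be small. Where some effect is already present at a late first measurement, the loss is towards understating Gateway's effect. A reader might infer that the trial's main conclusions are at risk; they are not, because the staff interviews, the referral analysis and the change-from-enrollment models do not rely on this baseline.

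**What to change.** 1. Reconcile the Gateway-attendance route in 5.1 (Veteran involvement and Characteristics) with the implementation text in 5.1 and with 5.2: either describe how and when such women are approached, or remove the route.
2. In 5.5, record for each woman the dates of the first survey, the first interview and the first Gateway meeting.
3. In 5.6, for the Gateway impact assessment only, count a survey or interview as baseline only if it was completed before the first Gateway meeting. Report how many women had a later first measurement and keep them as a separate group in the qualitative comparison. For any survey-based change score, show the result with and without them.

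The cost is a few sentences and three dates. The facilitator already fills in a tracking sheet at the group meeting; the sponsor should confirm that it captures the date. The downside is fewer women in the change assessment and possible selection, since women measured late may differ from those measured early. Showing survey results both ways, and keeping the late group visible in the qualitative work, makes that trade-off open to the reader.

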The CV Toolkit includes four elements: (1) Patient education/activation tools, such as informational posters and fliers about women's CV risk, including information about MyHealtheVet website resources. To activate patients to discuss CV risk with their providers, we developed a CV worksheet (Appendix 6) for patients to fill out at check-in to collect information about family history of CVD, pregnancy/gestational history, and smoking status, and to help patients formulate/document any questions regarding their CV risks that they would like to discuss during their visits. The goal is to help make CV risk discussion a priority for women before they enter the exam room. (2) A CV risk assessment computerized template systematically captures CVD risk factor history and data from the medical record, and provides open fields for the provider to enter any relevant information from the patient worksheet and the clinic visit (e.g., goals and decisions). The template also includes embedded links to locate CV guideline documents. Based on feedback from clinical teams at two GLA sites, the template includes data from the current visit as well as the last three entries in the medical record (automatically generated by the template) such as weight, blood pressure, and cholesterol lab results. This enables the provider to look at trends in risk factors without having to search the chart. The information is stored as a standard outpatient note in the patient's medical record (in CPRS) and is readily accessible (and searchable) at future visits so that CV risk status will be an ongoing discussion. Referral options are also included on the template, including referral to the *Gateway to Healthy Living* program, so the template will be a shared template available for other providers to access (e.g. health coach, dietitian, specialist, etc.) to review when the patient comes for the referral. (3) Provider information and education programs as well as referral tools to internal services (e.g., women's MOVE! program, smoking cessation clinics, dieticians, health coaches, pharmacists and CV or mental health specialists as needed). (4) The *Gateway to Healthy Living* program tailored to Women Veterans is a facilitated group meeting that occurs in a structured format with personalized goal setting and identification of key services available at the local site to assist with lifestyle changes necessary for patient-targeted CV risk reduction. In addition to the structured group, it includes at least two follow up phone calls from the facilitator (typically a health coach or health promotion disease prevention specialist) for support, reinforcement of lifestyle changes, brainstorming of barriers, and steps toward goal realization.

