**Quantitative Analysis:** We will use descriptive and inferential statistics to understand variations in the measures described above. For patients, we will conduct bivariate analysis to examine variations in outcomes (CV risk factor control, cardiac event or procedure, etc.) by those who participated in the *Gateway to Healthy Living* program, versus those who received a referral to a different program/service, and those who received no referral. For providers, we will examine differences in their patient panel (e.g. those with CV risk factors under control at follow-up) by their engagement in the CV toolkit program. To evaluate the CV toolkit, we will use the nonrandomized stepped wedge design, a generalized mixed model coupled with an allowance for nonrandom effects, to evaluate the implementation across the providers at four sites. The intervention will be defined as “turning on” when a provider first engages in the CV toolkit (first

uses the CV template). We will model the effect of the implementation of the CV toolkit intervention on referral rates, while controlling for organizational level, provider level and patient level covariates.

**Impact-focused evaluation:** Secondary aims focus on factors that empower Women Veterans to engage in and benefit from care. We will use generalized linear mixed models (GLM) to evaluate a) cross-sectional relationships of patient activation, health-related quality of life, and care experiences at enrollment, with provider and site characteristics, adjusting for patient social and demographic characteristics; and b) prospective changes in patient activation, health-related quality of life, and care experiences from enrollment to 6-month follow-up, adjusting for patient, provider, and site characteristics. We will also construct multi-level mediation and moderation models to explore whether engagement-related factors such as patient activation, strength of treatment preferences, or the communication subscale of the CAHPS are associated with greater benefit from or satisfaction with care.

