**Power Analysis:** Our goal with the power analysis was to ascertain the number of providers who would need to “turn on” the intervention (i.e., the number of PCPs who use the CV template, as well as the minimum number of patients that would need to be exposed to the care model. Consistent with our nonrandomized stepped wedge design, the power analysis presented here is for a 3-level hierarchical linear model where patients are clustered within PCPs within sites. In the final analysis structure, patients are the Level 1 units, the timing of PCP template use/referrals represents Level 2 units, and sites are the Level 3 units. The outcome of interest for CV Toolkit is the number of referrals to services (e.g. *Gateway to Healthy Living* and other services). The outcome is binary (referred/retained vs. not), and measured at the patient level (Level 1). Treatment effect is measured at Level 2, i.e., timing of when the PCPs turn on. Parameters required for calculating power are: alpha ( $\alpha$ ) = 0.05, sample size of patients clustered within referring PCPs ( $n$ ) = at least 260 (based on prior work), the number of sites ( $K$ ) = 4, the Plausible for Retention among those with low utilization (PI) = 5% to 85%, and Effect Size Variability (ESV) = medium or 0.05. Based on the resulting power curve, we need at least 8.78 (rounded to 9) referring PCPs per site to achieve power at 0.80. Our power analyses assume that the treatment effect is linear over time, i.e. patients that are retained longer have proportionally better outcomes. While selected details of the resulting dose response curve may vary, sensitivity analyses demonstrate a reasonable approximation enabling detection of treatment effects.

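### The CV template both marks the start of intervention time and is a named source for referral rates; if template-only referrals count, recording changes with exposure and the toolkit effect can be inflated

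*Combined protocol and SAP*

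**What the plan says.** The referral outcome and its sources appear in several places.

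- **Source of the outcome.** Section 5.1, Veteran involvement and Characteristics: "We will also use medical record data (CPRS template data and CDW data) to evaluate the roll-out of the intervention and the referral rates". Two sources are named for two purposes, without saying which serves which. The data are to cover all women seen by the study providers.
- **A second wording.** The Study Design paragraph of 5.1 uses administrative data from CPRS and CDW "to capture use of the CV toolkit (CPRS template) and referrals to preventive services". Here the template is attached by parenthesis to toolkit use.
- **What the template holds.** In the description of toolkit elements: "Referral options are also included on the template". In the description of the visit, patient and provider settle the next step (Gateway, another referral, or waiting), and "the provider will document the action plan in the template".
- **What defines exposure.** Section 5.6, Quantitative Analysis, starts the intervention "when a provider first engages in the CV toolkit", glossed there as first use of the template.
- **What is modelled.** The same paragraph: "We will model the effect of the implementation of the CV toolkit intervention on referral rates". The Power Analysis treats the outcome as binary at patient level.
- **The comparison.** In the stepped-wedge description, "sites act as their own controls in an evaluation that compares sites pre- versus post-implementation", alongside a between-site comparison.

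The protocol does not define a referral by a type of record that exists both before and after turn-on. It does not say whether choosing a referral option on the template generates an order in CDW, and it plans no analysis with and without template-only entries.

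**The concern.** A before-and-after contrast needs the outcome to be recorded in the same way in both states. Here one named source of the outcome is a component of the intervention and essentially comes into being when exposure starts. A referral agreed in conversation and never ordered could go unseen in control time, yet become a searchable template entry in intervention time. Better recording would then be read as more referring.

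The design cannot correct for this. The planned covariates and the between-site comparison deal with adoption timing, secular trend and site differences. A change in recording that coincides with the exposure indicator is indistinguishable from the effect being estimated. Within this mechanism the error can only favour the toolkit, and more patients make a spurious effect more convincing. Referral is the outcome of the stepped-wedge evaluation, so the main quantitative conclusion is at stake.

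**Working it through.** **The plan's own figures.** The documents give no referral rate, no capture rate for CDW and no share of referrals that would appear only on the template. The one related figure, 8.78 referring PCPs per site for power 0.80, cannot be re-derived because no effect size is stated. This point does not rest on it.

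**Step 1. Apparent effect when the true effect is nil.** Assumptions, none from the documents:

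- r = true referral rate in both states, 20%
- c = share of referrals that CDW captures in either state
- t = share of those CDW misses that the template recovers after turn-on

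Observed control rate = r × c. Observed intervention rate = r × (c + (1 − c) × t).

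| c | t | Control | Intervention | Odds ratio |
|---|---|---|---|---|
| 100% | any | 20.0% | 20.0% | 1.00 |
| 80% | 0% | 16.0% | 16.0% | 1.00 |
| 80% | 10% | 16.0% | 16.4% | 1.03 |
| 80% | 50% | 16.0% | 18.0% | 1.15 |
| 80% | 100% | 16.0% | 20.0% | 1.31 |
| 60% | 50% | 12.0% | 16.0% | 1.40 |
| 60% | 100% | 12.0% | 20.0% | 1.83 |

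Last row: (0.20/0.80) / (0.12/0.88) = 0.2500 / 0.1364 = 1.83.

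**Step 2. A second parameterisation.** Let u be the share of true referrals found only on the template, all of them counted after turn-on (t = 100%, c = 1 − u). The apparent rate ratio is 1/(1 − u), whatever the true rate: 1.00, 1.11, 1.25 and 1.43 for u = 0, 10%, 20% and 30%. At an assumed 35% true rate, u = 10%, 20% and 30% lower the observed control rate to 31.5%, 28.0% and 24.5%, with odds ratios of 1.17, 1.38 and 1.66.

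**Step 3. Chance of a false positive.** A simulation used 36 PCPs (4 sites × 9), a before/after comparison stratified by PCP (Mantel-Haenszel), no secular trend, no true effect and 4000 runs. PCP rates varied on the logit scale with variance ((logit 0.85 − logit 0.05)/3.92)² = 1.425, which takes the protocol's 5% to 85% interval as a 95% range.

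| Patients per PCP per period | u = 0 | u = 10% | u = 20% |
|---|---|---|---|
| 4 | 4.8% | 12% | 34% |
| 25 | 4.3% | 48% | 96% |
| 100 | 5.1% | 96% | 100% |

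With a source common to both states (u = 0) the error rate stays near 5%. With u above zero it climbs with sample size, and the protocol intends to read the outcome for all women seen. These rates follow from the chosen u and are not evidence that u is large.

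**The case against.** The strongest reply is that the protocol can be read without the flaw. The Study Design paragraph ties the template to toolkit use and leaves referrals to CPRS and CDW generally. The outcome is to cover all women seen, and template records exist only for visits where it was used, so an all-patient rate must rest largely on general records. This stands in part. It makes the bias conditional, but neither passage excludes template-recorded referrals, and the other wording names template data alongside the referral rates.

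Three further objections stand and limit the point.

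- **A reader might infer that template-type referrals could never be seen in control time.** The documents do not go that far. Section 5.5 plans chart review and section 7.0 mentions patient charts, so a referral in an ordinary note could be found, although neither clearly applies this to every control-time patient. Other staff may also fill in the template, while a provider turns on at her or his own first use.
- **A reader might infer that some inflation is certain.** The documents give no share of template-only referrals. If every template referral also reaches CDW, the bias is zero. Women referred to Gateway are to be contacted at once, so those referrals are acted on. Section 5.6 also expects infrequent template users, which would keep recovery low.
- **A reader might conclude that template data should be barred from the outcome altogether.** That could introduce the opposite error: if providers refer through the template instead of by order, a CDW-only count loses real referrals in intervention time only.

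It might also be said that better documentation is itself a toolkit goal. The modelled outcome is nevertheless referral rates, and documentation can be reported as adoption or fidelity.

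**Conclusion.** The concern holds in conditional form. As worded, the plan allows the instrument that defines exposure to supply part of the outcome, and nothing in the design or model would correct for that. Whether the estimate is actually inflated depends on two things that the documents leave open: whether template entries count as referrals, and how many of them have no counterpart in CDW.

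Under an assumed 20% true rate and no true effect, the apparent odds ratio lies between 1.00 and 1.83. The lower end is as consistent with the documents as the upper. The text does not support saying that the plan does inflate the effect, or that the bias has a floor above 1.00. It does support fixing the measurement rule before the data are analysed, because otherwise a positive result could not be told apart from a change in record-keeping.

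**What to change.** In section 5.1 (Study Design, and Veteran involvement and Characteristics) and in section 5.6 (Quantitative Analysis):

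1. Define the primary stepped-wedge referral outcome from records available in both states: consult orders in CDW, and scheduled or completed visits at the listed services, applied identically before and after turn-on.
2. Assign template data to adoption and fidelity.
3. Report how many template-recorded referrals have no matching CDW order or visit. This estimates the quantity on which the bias depends.
4. Add a sensitivity analysis that counts template-only referrals as well.
5. State whether choosing a referral option on the template creates an order, and whether Gateway attendance, which the facilitator tracks, is visible in CDW.

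The cost is protocol and analysis wording, one matching table and one extra model run; CDW data are already planned. The downside is that some real referrals go uncounted in the primary outcome. If providers refer through the template instead of by order, that loss falls in intervention time and biases toward no effect. The matching table and sensitivity analysis would show this.
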